Outcomes	
  
 Characteristics	Total (N=180)	Characteristics	Total (N=180)	
   
 Age (years)		Race		
 
 n	180	American Indian/Alaskan Native	2 (<1%)	
 
 Mean (S.D.)	47.6 (10.6)	Black/African American	2 (1%)	
 
 Median	50.0	Native Hawaiian/Pacific Islander	1 (<1%)	
 
 Minimum	18	Asian	0	
 
 Maximum	65	White	169 (94%)	
 
 Gender		Other	6 (3%)	
 
 Male	1 (<1%)	Ethnicity		
 
 Female	179 (99%)	Not Hispanic or Latino	161 (89%)	
 
 Fitzpatrick Skin	Hispanic or Latino	19 (11%)	
 
 I, II, and III	I, II, and III	139 (77%)	
 
 IV and V	IV and V	41 (23%)	
  
	Characteristics	Total (N=180)	Characteristics	Total (N=180)	Age (years)		Race		n	180	American Indian/Alaskan Native	2 (<1%)	Mean (S.D.)	47.6 (10.6)	Black/African American	2 (1%)	Median	50.0	Native Hawaiian/Pacific Islander	1 (<1%)	Minimum	18	Asian	0	Maximum	65	White	169 (94%)	Gender		Other	6 (3%)	Male	1 (<1%)	Ethnicity		Female	179 (99%)	Not Hispanic or Latino	161 (89%)	Fitzpatrick Skin		Hispanic or Latino	19 (11%)	I, II, and III		I, II, and III	139 (77%)	IV and V		IV and V	41 (23%)
Characteristics	Total (N=180)	Characteristics	Total (N=180)																																																		
Age (years)		Race																																																			
n	180	American Indian/Alaskan Native	2 (<1%)																																																		
Mean (S.D.)	47.6 (10.6)	Black/African American	2 (1%)																																																		
Median	50.0	Native Hawaiian/Pacific Islander	1 (<1%)																																																		
Minimum	18	Asian	0																																																		
Maximum	65	White	169 (94%)																																																		
Gender		Other	6 (3%)																																																		
Male	1 (<1%)	Ethnicity																																																			
Female	179 (99%)	Not Hispanic or Latino	161 (89%)																																																		
Fitzpatrick Skin		Hispanic or Latino	19 (11%)																																																		
I, II, and III		I, II, and III	139 (77%)																																																		
IV and V		IV and V	41 (23%)																																																		

Effectiveness
 
The purpose of this study was to evaluate the safety and effectiveness of Restylane for soft tissue augmentation of the lips. The results confirm that Restylane is highly effective for adding fullness to both the upper and lower lips for at least 6 months.
 
The results of the blinded evaluator MLFS assessments of lip fullness are presented in the figure below for subject outcomes 8, 12, 16, 20, and 24 weeks.
 
Outcomes
 
Proportion (%) of MLFS Responders Measured by the Blinded Evaluator
 
  
 Week 8	Week 12	Week 16	Week 20	Week 24	
   
 ■ Restylane Treatment (%)	92.6	90.1	84.2	75.0	69.6	
 
 ■ No Treatment (%)	28.9	36.8	35.9	33.3	36.8	
  
 
p-value < 0.001 for all time points
 
Subjects assessed lip improvement at each time point after treatment with a 7-point non-validated GASI. When upper and lower lip outcomes were combined, the following percentage of Restylane subjects assessed themselves as improved or better from Baseline: 97.7% (Week 2), 99.2% (Week 4), 96.7% (Week 8), 91.7% (Week 12), 85.0% (Week 16), 76.1% (Week 20), and 74.1% (Week 24). No patients in the No Treatment group assessed themselves as improved from Baseline at any visit.
 
80% of the eligible subjects elected to receive re-treatment at Week 24 which suggests that subjects believed that the safety concerns associated with Restylane lip injections were less than the aesthetic value provided by the device.
	Week 8	Week 12	Week 16	Week 20	Week 24	■ Restylane Treatment (%)	92.6	90.1	84.2	75.0	69.6	■ No Treatment (%)	28.9	36.8	35.9	33.3	36.8																																				
Week 8	Week 12	Week 16	Week 20	Week 24																																																	
■ Restylane Treatment (%)	92.6	90.1	84.2	75.0	69.6																																																
■ No Treatment (%)	28.9	36.8	35.9	33.3	36.8																																																

MA-1300-13K												
Design Endpoints	A prospective, open label, single center, blinded evaluator study in 20 subjects											
	The effectiveness evaluation parameter was the Global Aesthetic Improvement Scale (GAIS) To assess the Incidence and severity of adverse experiences from Restylane when used in the lips											
A total of 20 subjects (2 male, 18 female) were enrolled and 19 subjects completed the study. One 80 year old subject died during the study due to cardio-respiratory arrest. Mean age was 52.8 years old. Seventeen subjects were white.												
At 12 weeks, 7/19 (37%) subjects were rated as Improved on their GAIS assessment by the Blinded Evaluator. At 12 weeks, all (100%) subjects rated themselves as Improved on their GAIS assessment.												
Parameter	N	n	Subjects with Lip Improvement	Percent	90% CI	p-Value ^a						
Lip Improvement Using the Blinded Evaluator's Assessment ^b	20	19	7	37%	(0.19, 0.58)	0.820						
Lip Improvement Using the Treating Investigator's Assessment	20	19	19	100%	(0.85, 1.00)	<0.001						
Lip Improvement Using the Subject's Assessment	20	17	17	100%	(0.84, 1.00)	<0.001						
Due to the protocol deviation, the five blinded evaluator's assessment was a photo assessment.												
Mean Volume Used												
Up		Statistic		Volume of Injection (mL)								
Upper		N		20								
		Mean (S.D.)		0.82 (0.30)								
		Median		0.73								
		Min, Max		0.06, 1.40								
Lower		N		20								
		Mean (S.D.)		0.88 (0.37)								
		Median		0.80								
		Min, Max		0.06, 1.80								
Total		N		20								
		Mean (S.D.)		1.69 (0.62)								
		Median		1.60								
		Min, Max		0.13, 3.20								

Confidential

HOW SUPPLIED

Revanesse is supplied in a disposable glass syringe with a Luer-Lok® fitting. *Revanesse* is co-packed with sterilized needle(s) as indicated on the carton, either 30 G x ½" or 29 G x ½".

A patient record label is a part of the syringe label. Remove it by pulling the flap marked with three small arrows. This label is to be attached to patient records to ensure traceability of the product.

The contents of the syringe are sterile.

The volume in each syringe and needle gauge is as stated on the syringe label and on the carton.

SHelf LIFE AND STORAGE

Revanesse must be used prior to the expiration date printed on the package.

Store at a temperature of up to 25° C (77° F). Do not freeze. Protect from sunlight. Refrigeration is not required.

Do not re-sterilize *Revanesse* as this may damage or alter the product.

Do not use if the package is damaged.

Immediately return the damaged product to Medicis Aesthetics Inc.

U.S. only

U.S. PATENT 5,827,937

Manufactured for

Medics Aesthetics Inc.

[name]

[name]

U.S.A.

[contact]

Manufactured by

Q-Med AB

[name]

[name]

Sweden

Made In Sweden

Revanesse and *Pertlane* are registered trademarks of HA North American Sales AB.

All other trademarks are the property of their respective owners.

* NOTE: This printer-friendly version has been modified to print on letter paper. The formatting, size, and location of text, diagrams, and tables may be different from the package insert.

Revised: October 2011
15100255

[figure not shown]
DIRECTIONS FOR ASSEMBLY

ASSEMBLY OF 30 G NEEDLE TO SYRINGE

For safe use of Restylane, it is important that the needle is properly assembled. Improper assembly may result in separation of the needle and syringe during implantation.

See pictures A through E.

1. Unscrew the tip cap (B) of the syringe carefully.
2. Grasp the narrow part of the needle shield loosely; mount the needle on the Luer-Lok (C) by turning it clockwise until you feel counterpressure.
3. Grasp the wider part of the needle shield firmly (D).
4. Press and turn the needle shield 90° (a quarter turn).
5. The quarter turn is necessary to lock the needle onto the syringe.
6. Remove the patient record label marked with three small arrows (E) and attach to patient chart.
7. Pull off the needle shield.

ASSEMBLY OF 29 G NEEDLE TO SYRINGE

Use the thumb and forefinger to hold firmly around both the glass syringe barrel and the Luer-Lok adapter. Grasp the needle shield with the other hand. To facilitate proper assembly, both push and rotate firmly.

PRE-TREATMENT GUIDELINES

Prior to treatment, the patient should avoid taking aspirin, nonsteroidal anti-inflammatory medications, St. John's Wort, or high doses of Vitamin E supplements. These agents may increase bruising and bleeding at the injection site.

TREATMENT PROCEDURE

1. It is necessary to counsel the patient and discuss the appropriate indication, risks, benefits and expected responses to the Restylane treatment.
2. Advise the patient of the necessary precautions before commencing the procedure.
3. Assess the patient's need for appropriate anesthetic treatment for managing comfort, i.e., topical anesthetic, local or nerve block.
4. The patient's face should be washed with soap and water and dried with a clean towel. Cleanse the area to be treated with alcohol or another suitable antiseptic solution.
5. Sterile gloves are recommended while injecting Restylane.
6. Before injecting, press rod carefully until a small droplet is visible at the tip of the needle.
7. Restylane is administered using a thin gauge needle (30 G x 1/2" or 29 G x 1/2"). The needle is inserted at an approximate angle of 30° parallel to the length of the wrinkle, fold, or lip. For the nasolabial folds, Restylane should be injected into the mid-to-deep dermis. For lip augmentation, Restylane should be injected into the submucosal layer; care should be taken to avoid intramuscular injection. If Restylane is injected too superficially this may result in visible lumps and/or bluish discoloration.
8. Inject Restylane applying even pressure on the plunger rod. It is important that the injection is stopped just before the needle is pulled out of the skin to prevent material from leaking out or ending up too superficially in the skin.
9. Only correct to 100% of the desired volume effect. Do not overcorrect. With cutaneous deformities the best results are obtained if the defect can be manually stretched to the point where it is eliminated. The degree and duration of the correction depend on the character of the defect treated, the tissue stress at the implant site, the depth of the implant in the tissue and the injection technique.

10. Typical usage for each treatment session is specific to the site as well as wrinkle severity. In a prospective study of midface wrinkle correction, the median total dose was 3.0 mL. Based on U.S. clinical studies, the maximum recommended dose per treatment is 6.0 mL. For the nasolabial folds and 1.5 mL per lip per treatment.
11. Note The correct injection technique is crucial for the final result of the treatment.

INJECTION TECHNIQUES

1. Restylane can be injected by a number of different techniques that depend on the treating physician's experience and preference, and patient characteristics.

[figure not shown]
2. **Serial puncture (F)** involves multiple, closely spaced injections along wrinkles or folds. Although serial puncture allows precise placement of the filler, it produces multiple puncture wounds that may be undesirable to some patients.

3. **Linear threading** (includes retrograde and antergrade) (G) is accomplished by fully inserting the needle into the middle of the wrinkle or fold and injecting the filler along the track as a "thread." Although threading is most commonly practiced after the needle has been fully inserted and is being withdrawn, it can also be performed while advancing the needle ("push-ahead" technique). To enhance the vermillion of the lip, the retrograde linear threading technique is the most advisable.

[figure not shown]
4. Serial threading is a technique that utilizes elements of both approaches.

5. **Cross-hatching** (H) consists of a series of parallel linear threads injected at intervals of five to ten mm followed by a new series of threads injected at right angles to the first set to form a grid. This technique is particularly useful in facial contouring when coverage of the treatment region needs to be maximized.

[figure not shown]
F. Serial Puncture

G. Linear Threading (includes retrograde and antergrade)

H. Cross-hatching

6. Note The correct injection technique is crucial for the final result of the treatment.

Dissection of the sub-epidermal plane with lateral movement of the needle, rapid flows (>0.3 mL/min), rapid injection or high volumes may result in an increase in short-term episodes of bruising, swelling, redness, pain, or tenderness at the injection site.

7. When the injection is completed, the treated site should be gently massaged so that it conforms to the contour of the surrounding tissues. If an overcorrection has occurred, massage the area firmly between your fingers, or against the underlying area to obtain optimal results.

8. If so called "blanching" is observed, i.e., the overlying skin turns a whitish color, the injection should be stopped immediately and the area massaged until it returns to a normal color.

9. If the wrinkle or lips need further treatment, the same procedure should be repeated until a satisfactory result is obtained. Additional treatment with Restylane may be necessary to achieve the desired correction.

10. If the treated area is swollen directly after the injection, an ice pack can be applied on the site for a short period. Ice should be used with caution if the area is still numb from anesthetic to avoid thermal injury.

11. Patients may have mild to moderate injection site reactions, which typically resolve in less than 7 days in the nasolabial folds and less than 14 days in the lip.

STERILE NEEDLE(S)

- Follow national, local or institutional guidelines for use and disposal of medical sharp devices. Obtain prompt medical attention if injury occurs.
- To help avoid needle breakage, do not attempt to straighten a bent needle. Discard it and complete the procedure with a replacement needle.
- Do not re-use used needles. Recapping by hand is a hazardous practice and should be avoided.
- Discard unshielded needles in approved sharps collectors.
- Restylane is provided with a needle that does not contain engineered injury protection. Administration of Restylane requires direct visualization and complete and gradual insertion of the needle making engineered protections infeasible. Care should be taken to avoid sharp exposure by proper environmental controls.

Ordering Information

Medics Aesthetics Inc. and its distributor, McKesson Specialty, are your only sources for FDA-approved Restylane. Purchasing from any other agent is illegal.

To order call [contact].

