8.3.2 Exclusion Criteria

Subjects who meet any of the following criteria will be excluded from the study:

1. Wrinkle Severity Rating Scale Score of ≤ 2 on the right or left nasolabial fold.
2. Women who are pregnant or lactating.
3. Received prior dermabrasion, facelift, or Botox below the orbital rim within 6 months (180 days) prior to entry into the study.

4. Previous tissue augmentation (bulking agents) for facial wrinkles and scars within 6 months (180 days) at the proposed injection sites.
5. Previous tissue augmentation with permanent implants.
6. Evidence of scar-related disease or delayed healing activity within the past 1 year.
7. Scars at the intended treatment sites.
8. History of keloid formation or hypertrophic scars.
9. Any infection or wound on the face.
10. Allergic history including anaphylaxis or multiple severe allergies to natural rubber latex or lidocaine.
11. Aspirin or nonsteroidal anti-inflammatory drugs within 1 week (7 days) prior to treatment.
12. Concomitant anticoagulant therapy, antiplatelet therapy, or history of bleeding disorders or connective tissue disorders.
13. Over-the-counter (OTC) wrinkle products or prescription wrinkle treatments within 4 weeks (28 days) prior to treatment and throughout the study.
14. Immunocompromised or immunosuppressed.
15. Clinically significant organic disease including clinically significant cardiovascular, hepatic, pulmonary, neurologic, or renal disease or other medical condition, serious intercurrent illness, or extenuating circumstance that, in the opinion of the investigator, preclude participation in the trial.
16. Received any investigational product within 30 days of signing the Informed Consent Form.
17. Facial tattoo that may interfere with diagnosis.
18. Systemic (oral/injectable) corticosteroids or immunosuppressive medications within 30 days prior to treatment and topical steroids on the face within 14 days prior to treatment start and throughout the study.

8.3.3 *Subject Withdrawal Criteria*

A subject may withdraw from the study at any time for any reason.

A subject will be withdrawn from the study if his/her safety or well-being is determined to be at risk. Withdrawal will be made at the discretion of the investigator or at the subject's request.

A subject must withdraw from the study for any of the following reasons:

- The subject or legal representative withdraws consent
- The subject's product code is unblinded
- There is a significant protocol violation

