8.4.7 Prior and Concomitant Medications/Treatments

All medications and other treatments taken by the subject within 6 months before Visit 1/Day 1 and during the study are to be recorded on the CRF using their generic name, if known, with the corresponding indication. The medications to be recorded include prescription and OTC medications and dietary supplements. All medications taken on a regular basis, including vitamins, aspirin, and acetaminophen, should be recorded prior to first use of the study medication.

The use of any concomitant medication must relate to the subject's documented medical history, prophylaxis, or an AE.

8.4.7.1 Medications, Supplements, and Other Substances Prohibited Before Study Entry and During the Study

The medications prohibited prior to Visit 1/Day 1 are listed in the exclusion criteria ([Section 8.3.2](#)).

Subjects will be advised to avoid the following for the duration of the study:

- Botox® in the study treatment areas
- Any chemical peel (light, medium or deep) in the study treatment areas
- Soft tissue augmentation anywhere on the face
- Dermabrasion or laser abrasion anywhere on the face
- Silicone injections or implants anywhere on the face
- Facial wrinkle therapies, including Accutane® and Renova®
- Aesthetic facial surgery (i.e., facelift)
- Oral corticosteroids or immunosuppressive medications
- Topical corticosteroids on the face

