8.4.7.2 Concomitant Medications, Supplements, and Other Substances Allowed During the Study

Permitted medications/treatments include any concomitant medication/treatment not listed in the exclusion criteria ([Section 8.3.2](#)).

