8.6.11 Evaluation for Touch-up

If the iGAI score = 3 or 4 at Visit 2/Week 1 a touch-up treatment will be administered.

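### Two of the four agents that the appended Restylane directions say to avoid before treatment, St. John's Wort and high-dose vitamin E, are not restricted before the Day 1 injection or the Week 1 touch-up

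*Protocol*

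**What the plan says.** The pre-treatment guidelines in the Restylane insert (Protocol, Appendix 15.2) begin: "Prior to treatment, the patient should avoid taking aspirin, nonsteroidal anti-inflammatory medications". The same sentence goes on to St. John's Wort and ends "or high doses of Vitamin E supplements. These agents may increase bruising and bleeding at the injection site".

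Exclusion criterion 11, identical in the Synopsis and Section 8.3.2, reads: "Aspirin or nonsteroidal anti-inflammatory drugs within 1 week (7 days) prior to treatment".

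Three further provisions decide what happens to an agent that criterion 11 does not name:

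- Section 8.4.7.1: "The medications prohibited prior to Visit 1/Day 1 are listed in the exclusion criteria". It adds a list of things to avoid for the whole study.
- Section 8.4.7.2: "Permitted medications/treatments include any concomitant medication/treatment not listed in the exclusion criteria".
- Section 8.4.7: concomitant medication must relate to "documented medical history, prophylaxis, or an AE". On supplements it says: "The medications to be recorded include prescription and OTC medications and dietary supplements".

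A second injection session can follow within days. Section 8.6.11 says: "If the iGAI score = 3 or 4 at Visit 2/Week 1 a touch-up treatment will be administered".

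**The concern.** The comparator's insert groups four agents and gives one shared reason for avoiding them. The protocol turns two of them into a 7-day washout, is silent on the other two, and gives no reason for the split. The heading of Section 8.4.7.1 mentions supplements, yet its list contains neither St. John's Wort nor vitamin E.

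What is at stake is avoidable local harm. Section 8.4.3 describes bruising as the commonest side effect at this site, usually gone in 5 to 7 days. Section 9.5 has injection-site reactions tabulated by product and severity. Section 8.10 allows the study to be stopped if the rate of anticipated events, bruising among them, is judged too high at weekly review. A precaution that the comparator's own label supports is therefore worth having, even if its effect is small.

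**Working it through.** The plan gives no figure on this point, so the check is mainly a comparison of texts.

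**Coverage of the four agents**

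| Agent in the Restylane pre-treatment guidelines | Criterion 11 | Other 17 exclusion criteria | 9 items in Section 8.4.7.1 |
|---|---|---|---|
| Aspirin | yes | – | – |
| NSAIDs | yes | – | – |
| St. John's Wort | no | not named | not named |
| High-dose vitamin E | no | not named | not named |

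Named: 4. Covered: 2. Not covered: 4 − 2 = 2. The nearest other criterion, number 12, concerns anticoagulant and antiplatelet therapy and bleeding or connective tissue disorders. It names neither supplement.

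**Does anything else close the gap?**

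- *Before Day 1.* Section 8.4.7.1 places the pre-study prohibitions in the exclusion criteria. Neither agent is there, so neither is prohibited.
- *Between Day 1 and the touch-up.* Section 8.4.7.2 permits what the exclusion criteria do not list, so both are allowed.
- *Documented reason.* A subject who takes either supplement for a recorded condition or as prophylaxis meets the Section 8.4.7 requirement. It limits use but does not bar it.
- *Recording.* At Visit 1, medications are recorded at step 4, before randomization (step 8) and treatment (step 9) (Section 8.7.1). The site has the information, but no rule tells it to act. At Visit 2, concomitant medications are assessed, again with no consequence attached (Section 8.7.2).
- *Revanesse Ultra insert (Appendix 15.1).* It warns of more bruising and bleeding with the same four agents, but only as something to be aware of. It does not say to avoid them.

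**Length of the abstention under the fix**

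Visit 2 is Day 7 ± 2, that is Day 5 to Day 9, or 5 − 1 = 4 to 9 − 1 = 8 days after Day 1. With 7 days before Visit 1, the total is 7 + 4 = 11 to 7 + 8 = 15 days.

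**Subjects touched by the rule**

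The documents do not say how many subjects use these supplements. Assuming 1% to 10% (an assumption, with no source in the documents): 0.01 × 163 = 1.6 and 0.10 × 163 = 16.3, or about 2 to 16 of 163. This counts subjects who would need advice or rescheduling. It does not measure harm.

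**Size of the added risk**

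This cannot be computed. The insert says only that the agents may increase bruising and bleeding, and it defines neither a high dose nor a washout period. The 47% to 78% bruising rates in Section 8.9.4.3 are general Restylane rates, not an increment due to either supplement.

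**The case against.** The strongest case is that this is within the sponsor's discretion. The inserts are advice, and the Restylane contraindications name neither supplement. The protocol also departs from the insert elsewhere: it rules out topical anesthetic (Section 8.4.3) where the insert asks the injector to assess the need for anesthesia, and it excludes anticoagulant and antiplatelet users where the insert advises caution. Both inserts are appended, Section 6.1 points to them and to the consent documents for risks, and supplements are recorded before injection. The consent pages are not in the copy at hand and may carry the advice.

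This stands in part. It rules out calling the omission a contradiction or a label violation, which a reader might infer from the words of the insert. It does not remove the gap: appending a label, recording use and possibly mentioning it at consent do not restrict anyone.

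A second objection concerns the remedy and stands in full. It is tempting to add both supplements to criterion 11. But Section 9.1 requires the inclusion and exclusion criteria to be met for both the mITT and the PP population. A user discovered after randomization would then leave both efficacy populations for a reason with no evident bearing on WSRS, and Section 8.3.3 requires withdrawal for a significant protocol violation. The remedy should therefore be a precaution and not an exclusion criterion.

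Third, a reader might extend the precaution to the Week 24 retreatment. Only Revanesse Ultra is injected then, and its insert warns without saying to avoid, so the appended directions do not support that extension.

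Finally, the remedy treats the supplements differently from aspirin and NSAIDs between Visits 1 and 2. That is deliberate: Section 8.9.4.3 reports injection-site pain in 57% to 76% of Restylane subjects, and a ban in that week would take away pain relief.

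**Conclusion.** The point holds as a minor, optional improvement. Before the Day 1 injection and the Week 1 touch-up, the protocol in effect permits two of the four agents that its appended comparator directions say to avoid. The likely benefit of covering them is slightly less bruising and bleeding, and the documents give no basis for a number.

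A reader might infer that the omission biases the product comparison or weakens the non-inferiority test. The documents do not support that. Each subject receives both products, so an agent acting systemically should mainly affect both folds alike, and nothing in the documents links bruising or bleeding to WSRS at Week 24. No sample size, power or error rate changes.

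The conclusion rests on the protocol text as shown. If the consent form already tells subjects to avoid these supplements, the practical gap is smaller, though the protocol would still set no rule.

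**What to change.** Leave criterion 11 unchanged. Add a separate paragraph below the list in Section 8.4.7.1, because that list runs for the whole study:

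> Subjects should avoid St. John's Wort and high-dose vitamin E supplements (dose threshold set by the sponsor's medical staff) for 7 days before the Visit 1 injection and until the touch-up decision at Visit 2. A subject found at the Visit 1 medication review to have used either within 7 days is rescheduled before randomization. Use is not in itself an eligibility violation or grounds for exclusion from the mITT or PP population.

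The 7-day period is borrowed from criterion 11, since the insert gives none. The vitamin E threshold must be set before the text is issued, or practice will vary by site.

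The cost is one paragraph, one dose threshold, and a delay of up to 7 days for a few users, as an aspirin or NSAID user already faces. Supplements are already recorded, so no new data collection is needed.
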